9.4.3.3 Stool Consistency

Stool Consistency will be calculated using the BSFS. The BSFS is recorded at approximately the same time each day. Subjects will be asked for the number of bowel movements in the previous

24 hours. Subjects will use the BSFS to score the worst stool in the preceding 24 hour period. Extreme stool consistency is defined as 1, 2, 6, or 7 on the BSFS, while BSFS scores of 3,4 and 5 are considered within the normal range. The BSFS scores will be grouped as 1,2 (Group 1), 3,4,5 (Group 2) and 6,7 (Group 3). For participants in the IBS-D and IBS-M subtypes, a stool consistency response is defined as having a greater than or equal to 50% reduction from baseline (Phase 1) in the number of days with a BSFS score of 6 or 7. Stool consistency response for the IBS-D and IBS-M subtypes will be analyzed with methods similar to those used to assess the primary endpoint described in [Section 10.4.2](#).

Additionally, change from baseline in the percentage of days with a BSFS score in Group 2 will be analyzed at all 4-week assessment time periods with a mixed effects repeated measures model (MMRM). The model will include treatment, time period, IBS subtype, gender, and treatment by time period interaction as fixed effects and subject as a random effect. The unstructured covariance matrix will be used to model the within-subject correlation. Using the ESTIMATE and LSMEANS statements within PROC MIXED, the model-based LS means and LS mean differences (GDH minus comparator) and associated 95% CIs for each time period and overall will be estimated.

The percentage of the number of days with a BSFS score in each BSFS group will be summarized descriptively by treatment, IBS subtype and time period.

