9.4.3.4 Stool Frequency

Analyses of daily stool frequency will only include participants with IBS-C.

Daily stool frequency will be calculated as the average number of stools per day during each 4-week assessment period. Only days during which an assessment is recorded will be included in the calculation of average stool frequency.

For participants in IBS-C subtype, a stool frequency response is defined as an increase from baseline (Phase 1) of ≥ 1 bowel movement per day. Stool frequency response for IBS-C participants will be analyzed with methods similar to those used to assess the primary endpoint described in [Section 10.4.2](#).

Change from baseline and at-assessment values of daily stool frequency will be analyzed at all 4-week assessment time periods with a mixed effects repeated measures model (MMRM). Separate models will be performed for each IBS subtype. The model will include treatment, time period, gender, and treatment by time period interaction as fixed effects and participant as a random effect. The unstructured covariance matrix will be used to model the within-participant

correlation. Using the ESTIMATE and LSMEANS statements within PROC MIXED, the model-based LS means and LS mean differences (GDH minus comparator) and associated 95% CIs for each time period and overall will be estimated.

Daily stool frequency will be summarized descriptively by treatment and time period.

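### The IBS-M stool consistency responder rule counts only loose days, so by the protocol's own definition of extreme stool it can misclassify mixed-subtype subjects in both directions

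*Combined protocol and SAP*

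**What the plan says.** Section 9.4.3.3 of the protocol first sets up a two-sided scale: "Extreme stool consistency is defined as 1, 2, 6, or 7 on the BSFS". Days scored from 3 to 5 count as normal. The section then sorts the scores into a hard group (1-2), a normal group (3-5, called Group 2) and a loose group (6-7). There is one score per day: "Subjects will use the BSFS to score the worst stool in the preceding 24 hour period".

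The responder rule uses only the loose end and is shared by two subtypes: "For participants in the IBS-D and IBS-M subtypes, a stool consistency response is defined as" at least a 50% "reduction from baseline (Phase 1) in the number of days with a BSFS score of 6 or 7". No condition is placed on days scored 1 or 2. The comparison follows the primary method, which in Section 9.4.2 is a Cochran-Mantel-Haenszel (CMH) test adjusted for IBS subtype and gender.

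Two further analyses are planned in the same section. One is a repeated-measures model (MMRM), in which "change from baseline in the percentage of days with a BSFS score in Group 2 will be analyzed". The other is a descriptive table of the share of days in each of the three groups, by treatment, subtype and period.

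Section 4.2.2 lists stool consistency for IBS-D and IBS-M among the secondary efficacy endpoints. Section 9.4.3.4 states: "Analyses of daily stool frequency will only include participants with IBS-C". The consistency rule is therefore the only stool responder rule that applies to IBS-M.

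**The concern.** Section 3.1 names IBS-M as the mixed subtype, set apart from the constipation and diarrhoea subtypes. A rule that looks only at loose days measures one half of that disturbance. Success can be recorded when one kind of extreme stool has merely replaced the other, and real improvement at the hard end earns no credit.

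What is at stake is the meaning of the IBS-M response rate, and of the pooled IBS-D/IBS-M comparison it feeds. Two planned analyses of the same endpoint can also point different ways for the same subject, and the plan does not say which would govern the interpretation.

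**Working it through.** **Plan's own figures.** The plan gives no expected rate, sample size or power for stool consistency response. Its only power statement (Section 9.2) concerns the primary endpoint. With 150 per arm, 44% against 26% and two-sided 5%, a pooled-variance calculation gives 90.9%, which agrees with the stated minimum of 90%. Nothing below depends on it.

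**Rules compared.** Let H, N and L be the numbers of hard (1-2), normal (3-5) and loose (6-7) days in a 28-day period, with subscript 1 for Phase 1 and 3 for Phase 3.

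- As written (Section 9.4.3.3): response if (L1 − L3)/L1 ≥ 50%.
- On the section's own definition of extreme stool: response if [(H1 + L1) − (H3 + L3)]/(H1 + L1) ≥ 50%.

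If d loose days become hard days, L falls by d while H + L does not move. The rule as written is met as soon as d ≥ L1/2, with no change in extreme or normal days.

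**Illustration.** The diaries are assumed, because the documents give no stool-score distribution for IBS-M. Every day is taken to have a scored stool. Phase 1 is 8 hard / 12 normal / 8 loose, so extreme days are 8 + 8 = 16.

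| Phase 3 (hard/normal/loose) | Fall in loose days | Response as written | Extreme days | Fall in extreme days | Response on extreme days | Change in normal days |
|---|---|---|---|---|---|---|
| 12/12/4 | (8−4)/8 = 50% | yes | 16 to 16 | 0% | no | 0 |
| 14/10/4 | (8−4)/8 = 50% | yes | 16 to 18 | −12.5% (a rise) | no | −2/28 = −7.1 points |
| 0/20/8 | (8−8)/8 = 0% | no | 16 to 8 | 50% | yes | +8/28 = +28.6 points |
| 8/16/4 | (8−4)/8 = 50% | yes | 16 to 12 | 25% | no | +4/28 = +14.3 points |
| 4/20/4 | (8−4)/8 = 50% | yes | 16 to 8 | 50% | yes | +8/28 = +28.6 points |

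Rows 1 and 2 are successes without any fall in extreme days. Row 3 is a failure although extreme days halve. Row 4 is a subject who improves only at the loose end and would lose responder status under the alternative. Row 5 is a response on both rules. Neither rule contains the other.

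**How many subjects the rule covers.** Section 7.2.2 aims for at least about 25% of randomized subjects in each major subtype: 0.25 × 380 = 95 in IBS-M. Only IBS-D and IBS-M enter this analysis, so the IBS-M share of it is larger. Assume both subtypes lie between that section's approximate figures of 90 and 144 (144 is a temporary pause on screening, not a fixed ceiling). IBS-M is then between 90/234 = 38% and 144/234 = 62% of the analysed subjects. These are subjects to whom the rule applies, not subjects it misclassifies.

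**The case against.** The strongest reply is that the information is already analysed. Among scored days, the percentage in Group 2 is 100 minus the percentage of extreme days. The MMRM is therefore an inferential analysis of extreme days at every 4-week period, with confidence intervals. Section 4.2.2 words the endpoint as an overall mean change, and this model is closer to that than a responder rate is. It would credit none of the swings in rows 1 and 2 of the table. The descriptive summary by subtype would show a rise in hard days, and Section 9.4.8 plans subgroup analyses by subtype. All of this stands, and it limits the chance of a misleading overall reading. A reader might infer that the extreme-stool definition is never used; that is too strong, because its complement is modelled. None of it changes who counts as a responder, however, and the model has no treatment-by-subtype term.

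It can also be said that a loose-stool response is a coherent choice, and that the section never equates response with fewer extreme days. Section 5.2.3 adds that the primary and key secondary endpoints come from regulatory guidance. That guidance is not part of the documents, so whether this rule comes from it cannot be checked. The protocol gives no reason for applying a loose-only rule to the mixed subtype, and its own definition of extreme stool suggests a two-sided one.

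A reader might further infer that the rule favours an arm that merely slows the bowel. The documents do not support this: both arms are recorded behavioural programmes on the same platform, and nothing attributes such an effect to either. Without a difference between arms in such swings, the consequence is noise in neither arm's favour.

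**Conclusion.** The point holds as a matter of definition. For IBS-M, the responder rule can count a loose-to-hard swing as success with extreme days unchanged or even increased, and can count a halving of extreme days as failure. Misclassification here is judged against Section 9.4.3.3's own definition of extreme stool.

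The rule applies to about 95 or more randomized IBS-M subjects, roughly 38-62% of those in the stool consistency responder analysis under the enrolment assumption above. How often misclassification would occur, how far response rates would move, and in which arm cannot be determined from the documents; the diaries show only that it is possible.

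A reader might take this as a threat to the trial's conclusion. It is not: the endpoint is secondary and plays no part in the success criterion of Section 9.4.2. The change is a cheap improvement.

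**What to change.** Before unblinding, amend Section 9.4.3.3 and carry the change into the SAP, which Section 9 says will be finalized before treatment assignments are revealed:

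- Keep the present rule (days scored 6 or 7) for IBS-D.
- For IBS-M, define response as at least a 50% reduction from Phase 1 in days scored 1, 2, 6 or 7.
- Analyse both in the planned CMH test. It is adjusted for subtype, so each definition is compared between arms within its own strata.
- Report the loose-only version for IBS-M alongside, and show response by subtype as well as pooled.

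The cost is a sentence or two of text and one extra analysis. The full 1-7 scale is already recorded daily (Section 8.4.3), so no new data are needed. There are two downsides. IBS-M response rates may move up or down in either arm, since the two-sided rule is not uniformly stricter (rows 3 and 4 of the table). The pooled IBS-D/IBS-M rate will also combine two subtype-specific definitions, which is why the results by subtype should accompany it.

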9.4.3.4 Stool Frequency

Analyses of daily stool frequency will only include participants with IBS-C.

Daily stool frequency will be calculated as the average number of stools per day during each 4-week assessment period. Only days during which an assessment is recorded will be included in the calculation of average stool frequency.

For participants in IBS-C subtype, a stool frequency response is defined as an increase from baseline (Phase 1) of ≥ 1 bowel movement per day. Stool frequency response for IBS-C participants will be analyzed with methods similar to those used to assess the primary endpoint described in [Section 10.4.2](#).

Change from baseline and at-assessment values of daily stool frequency will be analyzed at all 4-week assessment time periods with a mixed effects repeated measures model (MMRM). Separate models will be performed for each IBS subtype. The model will include treatment, time period, gender, and treatment by time period interaction as fixed effects and participant as a random effect. The unstructured covariance matrix will be used to model the within-participant

correlation. Using the ESTIMATE and LSMEANS statements within PROC MIXED, the model-based LS means and LS mean differences (GDH minus comparator) and associated 95% CIs for each time period and overall will be estimated.

Daily stool frequency will be summarized descriptively by treatment and time period.

9.4.3.5 IBS-QOL

The IBS-QOL is a 34-item questionnaire. The items are summed and transformed to a 0-100-point scale. Higher scores indicate better IBS quality of life.

Change from baseline and at-assessment values of IBS-QOL score measured at the Baseline visit, week 16, week 38, and week 64 will be analyzed with a MMRM. The model will include treatment, week, IBS subtype, gender, and treatment by week interaction as fixed effects and subject as a random effect. The unstructured covariance matrix will be used to model the within-subject correlation. Using the ESTIMATE and LSMEANS statements within PROC MIXED, the model-based LS means and LS mean differences (GDH minus comparator) and associated 95% CIs for each week and overall will be estimated.

IBS-QOL score will be summarized descriptively by treatment and week.

9.4.3.6 Workplace Presenteeism and Absenteeism

The Workplace Productivity and Activity Impairment Questionnaire (WPAI) is a 6-question survey of presenteeism and absenteeism and it will be measured at the Baseline visit, week 8, 16, 38, and 64.

Percent overall work impairment due to problem and percent activity impairment due to problem will be analyzed similarly to IBS-QOL.

Percent work time missed due to problem, percent impairment while working due to problem, percent overall work impairment due to problem and percent activity impairment due to problem will be summarized descriptively by treatment and week.

9.4.4 Exploratory Analyses

The following exploratory endpoints will be detailed out in the statistical analysis plan.

- PHQ-4
- TIS
- IBS-AR
- Blinding question
- Satisfaction questionnaire

- Treatment adherence
- Concomitant medication usage

9.4.5 Safety Analyses

All AEs will be coded to System Organ Class (SOC) and Preferred Term using Medical Dictionary for Regulatory Activities (MedDRA). The number and percentage of subjects that experience at least one AE, grade 3-5 AEs, related AEs, SAEs, and related SAEs will be summarized by treatment group. Additionally, AEs will be summarized by severity and relatedness.

9.4.6 Baseline Descriptive Statistics

Demographic and baseline characteristics will be listed and summarized descriptively by treatment group.

9.4.7 Planned Interim Analyses

There are no planned interim analyses.

9.4.8 Sub-Group Analyses

The primary and secondary endpoint analyses will be conducted in the following subgroups:

- Gender
- IBS subtype
- Age group (<=median, > median)
- Concomitant medication
 - On IBS drug therapy vs not on IBS drug therapy
 - IBS-C on IBS drug therapy vs IBS-C not on IBS drug therapy
 - IBS-D on IBS drug therapy vs IBS-D not on IBS drug therapy

Further details will be provided in the statistical analysis plan.

10 SUPPORTING DOCUMENTATION AND OPERATIONAL CONSIDERATIONS

10.1 Regulatory, Ethical, and Study Oversight Considerations

10.1.1 Informed Consent

Written informed consent must be obtained from all subjects prior to entry into the study. Written consent documents will embody the elements of informed consent described in the Declaration of Helsinki and the ICH Guidelines for GCP and will be in accordance with all applicable laws and regulations. The informed consent form describes the planned and permitted uses, transfers, and disclosures of the subject's personal and personal health information for purposes of conducting the study. The informed consent form further explains the nature of the study, its objectives, and potential risks and benefits, as well as the date informed consent are given. The informed consent form will detail the requirements of the subject and the fact that he or she is free to withdraw at any time without giving a reason and without prejudice to his or her further medical care.

The PI/Sponsor is responsible for the preparation, content, and IRB approval of the informed consent form. The informed consent form must be approved by the IRB. The informed consent must be written in a language fully comprehensible to the prospective subject. It is the responsibility of the investigator or delegated staff to explain the detailed elements of the informed consent form to the subject.

Curebase will use an electronic consent platform (eConsent) to facilitate the consent process. The eConsent will be introduced to subjects as part of an on-line pre-screening interview. The pre-screening process requires subjects to create an account and login that allows ongoing access to their secure Curebase platform account. Once subjects pass their pre-screening they will be able to review the eConsent, HIPAA Authorization, and the Experimental Subjects' Bill of Rights using their own personal electronic devices, like a phone, tablet, or computer. During the subject's review they will be provided an opportunity to discuss the content of the eConsent with study personnel via email or telephone.

Subjects will have the option to delay document signing and proceed to the study visit where they can further discuss the consent with the study physician prior to signing. Each subject will be required to electronically sign the study informed consent, HIPAA Authorization, and the Experimental Subjects' Bill of Rights before they are allowed to participate in the study. After signing each document, subjects will be sent digital PDFs of their documents for their personal records. The original informed consent form will be stored in the eCRF. In the case of revisions to the informed consent form, subjects will be contacted and revised eConsent forms must be reviewed and signed by subjects. The date the revised consent was obtained will be recorded with the eConsent.

10.1.2 Study Discontinuation and Closure

metaMe reserves the right to terminate or suspend the study at any time for any reason. Circumstances that may warrant termination or suspension include, but are not limited to:

- Determination of unexpected, significant, or unacceptable risk to subjects
- Insufficient compliance to protocol requirements
- Data that are not sufficiently complete and/or evaluable

Study may resume once concerns about safety, protocol compliance, and data quality are addressed, and satisfy the sponsor, IRB, and/or Food and Drug Administration (FDA).

10.1.3 Confidentiality and Privacy

Subject confidentiality and privacy are strictly held in trust by the participating investigators, their staff, and the sponsor and their interventions. Therefore, the study protocol, documentation, data, and all other information generated will be held in strict confidence. No information concerning the study or the data will be released to any unauthorized third party without prior written approval of the sponsor. All research activities will be conducted in as private a setting as possible.

Curebase, Inc. will prepare and maintain adequate and accurate electronic source documents designed to record all observations and other pertinent data for each subject screened or enrolled in the study. All data from subjects will be collected, managed, and securely stored by Curebase. Curebase stores all data in a secure cloud server (AWS) and complies with HIPAA and GDPR standards, including but not limited to: password protection, platform encryption, and 2-factor verification. Curebase takes as much action as possible to maximize the protection and security of subject's sensitive information. In order to maintain subject confidentiality, subjects will not be identified by name in any reports or study documents to be collected by the Sponsor (or designee), but will be identified by a clinic number and subject number.

metaMe Health, Inc. will collect and store PHI. This information is needed to correctly target treatment notification, treatment reminders, and to administer the treatment. There will be no data link between PHI and treatment allocation or data used to determine treatment compliance (see [Section 6.3](#)). metaMe Health stores all data in a secure cloud server (AWS) and complies with HIPAA and GDPR standards, including but not limited to password protection and platform encryption. To maintain subject confidentiality, subjects will not be identified by name in any reports or study documents to be collected by the Sponsor (or designee), but will be identified by a clinic number and subject number.

Refer to [Section 10.1.6](#) for additional information on how data will be collected and secured.

10.1.4 Clinical Monitoring

Curebase will provide clinical monitoring during the study to ensure that:

1. The rights and well-being of human subjects are protected
2. The reported study data are accurate and complete
3. The conduct of the study is in compliance with the currently approved protocol/amendment(s), with GCP, and with the applicable regulatory requirements.

Refer also to [Sections 11.1.5](#) and [11.1.6](#) for additional details.

10.1.5 Quality Assurance and Quality Control

Quality control (QC) procedures will be implemented beginning with the data entry system. Data QC checks will be remotely run on the database and shall be generated on an ongoing basis to verify the accuracy and integrity of data being collected. Any missing data or data anomalies will be communicated to the investigators for clarification and resolution.

Following written standard operating procedures (SOPs), the monitor will verify that the clinical study is conducted and data are generated, documented (recorded), and reported in compliance with the protocol, ICH GCP and applicable regulatory requirements.

The investigators will provide direct access to all study related records, source data/documents, and reports for the purpose of monitoring and auditing by the sponsor, and inspection by the relevant regulatory authorities.

10.1.6 Data Collection, Retention, and Monitoring

Investigators and their representatives will be required to complete a training on using the Curebase platform prior to working with subjects. Training material will include instructions on how to enter data correctly, how to enter protocol deviations and AEs, and how to modify and update the eCRF. Training of investigators and research personnel will be tracked by Curebase using study-specific activation logs. Following written SOPs, the study monitors will verify that the clinical study is conducted and data are generated, documented, and reported in compliance with the protocol, ICH GCP, and applicable regulatory requirements.

Study personnel will enter data collected during the baseline visit into the Curebase eCRF. If a correction is required for a subject's eCRF, the time and date stamp tracks the person entering or updating eCRF data and creates an electronic audit trail. The Investigators and Curebase are responsible for all information collected on subjects enrolled in this study.

Curebase will provide clinical monitoring during the study to ensure that:

1. The rights and well-being of human subjects are protected
2. The reported study data are accurate and complete
3. The conduct of the study is in compliance with the currently approved protocol/amendment(s), with GCP, and with the applicable regulatory requirements.

4. Correct coding of AEs, medical history, and concurrent medical conditions using the Medical Dictionary for Regulatory Activities (MedDRA). Drugs will be coded using the World Health Organization Drug Dictionary (WHO).

